2.3 Research Design

STAGE1

The publication of the LACC trial has caused a huge impact in the gynecology field, and the version 3.2019 NCCN guidelines no longer recommended laparoscopic surgery for patients with cervical cancer. However, the investigators reviewed data from our hospital for the last 8 years of laparoscopic radical cervical cancer surgery, which showed different results from the LACC trial. During the Global Clinical Scholar Research Training (GCSRT) program hosted by Harvard Medical School, the leader of the main center discussed with local clinical research experts about the ethical feasibility of redesigning the RCT study to validate the topic, and in the first draft of this project design was completed as part of the Capstone Project course plan, and the study design was recommended in the end-of-semester presentation.

STAGE2

According to the trial design, after the study passed by ethics, the research team started to try the protocol according to the design process and successfully recruited 84 subjects. At the beginning of the study design, the study mixed cervical cancer stages IA1 with LVSI, IA2, IB1, IB2, IIA1, IB3, and IIA2 in one trial. However, as the trial progressed, we found that the span of the trial stages was too large for a specific assessment of each stage and for guiding the specific procedure for each stage. Also, when we submitted the protocol, we received the same suggestion from the review responses.

STAGE3

This project is divided into three parallel studies based on the staging, LAUNCH 1 (IA1 with LVSI, IA2), LAUNCH 2 (IB1, IB2, IIA1), and LAUNCH 3 (IB3, IIA2). Previously we conducted a single-center study (study protocol registration number: ChiCTR1900025946) which included all above mentioned stages. There are 84 patients

enrolled in that study which will not be included in the current project, since those patients do not meet the randomization strategy of the current project.

STAGE4

This study intends to sample and collect intraoperative tumor tissues from tumor patients, and to conduct basic science research on the evaluation of genetic testing for specific tumor stages, which can be used to guide later treatments such as targeted or immune therapies. At the same time, we will conduct relevant histological studies on the molecular tissues related to tumors in order to find the pathogenesis pattern that may guide treatment.

III. Research methods

1. Study setup

This project is a multicenter study led by the Obstetrics and Gynecology Hospital of Fudan University, which is one of the first national clinical class I key specialties in China and a key discipline of the Ministry of Education. The Obstetrics and Gynecology Hospital of Fudan University undertakes the task of diagnosis and treatment of malignant tumors of the female reproductive system nationwide, with a leading annual volume of cervical cancer surgery and treatment in China. The clinical centers of this study includes Obstetrics and Gynecology Hospital of Fudan University (main center), Zhongshan Hospital affiliated to Fudan University, Renji Hospital of Shanghai JiaoTong University, Xinhua Hospital of Shanghai Jiao Tong University, Taizhou Hospital Affiliated Cancer Hospital of the University of Chinese Academy of Sciences and the First Hospital of Wenzhou Medical University (sub-centers). The CTU of the Clinical Trial Center of the Children's Hospital of Fudan University is responsible for statistical analyses. All these have provided adequate technical support and guarantee for the study.

2. Qualification criteria

2.1 Study subjects and study time

A total of 1104 patients diagnosed with cervical cancer (stage IB3 and IIA2) and meeting the enrollment criteria will be recruited from the aforementioned main center and sub-centers. This project is expected to be completed in 3 years (April 2021 to April 2024) from the date of formal ethical approval and completion of enrollment, and the patients will be followed-up for 5 years (April 2021 to April 2026).

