3.7.3 Post-treatment follow-up records

One week after the end of treatment.

- a) Record postoperative pathology results and corresponding follow-up treatment plan
- b) Review laboratory tests (e.g. blood and urine routine test, coagulation function, blood liver, kidney function, electrolytes, drainage fluid creatinine)
- c) Postoperative indwelling catheter for 3-6 weeks and review of residual urine when the catheter is removed
- d) Postoperative complications (lymphatic cysts, dysuria, vaginal bleeding)

Review every 3 months for 2 years after completion of treatment with:

- a) Imaging examinations (chest CT + pelvic enhancement MRI + upper abdomen enhancement MRI or PET-CT)
- b) Tumor indicators: SCC antigen test (SCCA) and CA-125
- c) HPV and TCT test (once a year after completion of treatment)
- d) Adverse events recording
- e) Assessment of quality of survival and quality of sexual life using the Quality of Survival Scale for Cancer Patients (EORTC QLQ-C30 v3.0), the Cervical Cancer Sexual Life Scale (EORTC QLQ-CX24), and the Patient Reported Clinical Outcome Assessment Scale for Cervical Cancer PRO147 (V1.0).

After 2 years, the study will be reviewed every 6 months until the end of the trial. The review will include gynecological examination, tumor indicators (SCC antigen detection (SCCA) and CA-125), TCT examination and HPV examination, imaging (chest CT + pelvic enhancement MRI + upper abdomen enhancement MRI or PET-CT), and adverse event records.

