Supplementary therapy will be administered according to the postoperative pathological findings of the patients. Those with high-risk factors who have positive parametrium will be supplemented with external pelvic irradiation therapy + cisplatin/carboplatin concurrent chemotherapy, those with positive vaginal margins will be selected for external pelvic irradiation therapy + retrovaginal radiotherapy + cisplatin/carboplatin concurrent chemotherapy, and those with positive pelvic lymph nodes will be treated with 1 course of systemic chemotherapy + external pelvic irradiation radiotherapy ± extended field radiotherapy adjacent to the abdominal aorta + cisplatin concurrent chemotherapy + 3-6 courses of adjuvant systemic chemotherapy after radiotherapy. Those with intermediate risk factors will be treated with external pelvic irradiation radiotherapy + cisplatin concurrent chemotherapy, and those with positive proximal margins will be treated with external pelvic irradiation radiotherapy EBRT + cisplatin concurrent chemotherapy + retrovaginal radiotherapy. Targeted immunotherapeutic agents such as bevacizumab and PD-1, which have just obtained some results in clinical studies, are not considered in this trial for the time being. It could be used according doctor's orders.

3.10 Outcome measurements:

- 1) Main outcome indicators: 5-year OS.
- 2) Secondary outcome measurements: 5-year PFS, refer to RECIST criteria.
- 3) Other outcome measurements: operation time, anesthesia time, intraoperative bleeding volume, intraoperative complications, postoperative complications, postoperative pain score, postoperative hospital stay, one-month postoperative survival quality, one-year postoperative survival quality, sexual quality of life.
- 4) Other evaluation parameters: patient's demographic characteristics, signs and symptoms, stage, pathological type, tumor site, comorbidities, medical history, length of hospital stay and cost.
- 5) This study intends to sample and collect intraoperative tumor tissues from tumor patients and evaluate specific tumor stages with genetic testing to guide later treatments such as targeted or immune therapies. Histological studies and molecular studies will also be conducted.

	Pre-phase	0-12 months	12-24 months	24-36 months	36-60 months
Meet the researchers	X				
Obtain IRB approval	X				
Funding application	X				
Enrollment of study patients		X	X	X	
Data monitoring		X	X	X	X
Data collection		X	X	X	X
Data analysis					X

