Summary and discussion					X

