3.12 Sample size

This study uses a non-inferiority trial design, and the primary outcome is the rate of OS at 5 years. The sample size is calculated based on the difference between the two groups of 5-year OS rate. The 5-year OS rate of the patients in the open surgery group is estimated to be 72% based on the previous clinical data from our hospital.

Based on the assumptions of (i) the 5-year OS rate of 72% in the open surgery group, (ii) a non-inferiority margin of 8%, (iii) 80% power, and (iv) a one-sided alpha of 0.025, the sample size estimation resulted in 495 subjects per group (calculated with SAS software, version 9.4). Considering a 10% drop-out rate and the randomization scheme with block size of 6, a total of 1104 subjects should be randomized (552 per group).

3.13 Recruitment methods:

The study team centers will advertise this study at their cervical cancer clinic. If the patients are interested, they will be further introduced in detail about the study background, randomization and surgical procedures, and the patients can voluntarily choose whether to participate in the trial. After patients sign the informed consent forms, members of the study team will review their eligibility according to the inclusion and exclusion criteria. Patients will then be randomized to receive either of the surgical

procedures. Finally, the patients will be followed up according to the follow-up schedule.

IV. Allocation, Blinding and Unblinding

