5.2 Data management (entry, coding, encryption and storage)

5.2.1 Entry and coding protocols:

A database for data management and entry is designed based on the finalized CRF form. This study uses RedCap, which was developed by a professional CRO data management team, and the project data entry and management will be handled by dedicated personnel. To ensure the accuracy of the data, double entry should be performed by two research members independently, and blind verification and statistical analysis should be performed after software verification and manual error correction. The database will be locked after accuracy confirmation. The locked data files then will be submitted to an independent third-party statistical team for analysis. The statistical analysis plan (SAP) is developed by the statistical team during the study subject inclusion process, and finalized after repeated discussions with the investigator team, and uploaded to the clinical trial registry website before the last patient data collection is completed at the study registry website, or submitted for publication with the protocol.

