5.3 Statistical methods

5.3.1 Outcome statistical methods

Statistical analysis of the study will be undertaken by the CTU of the Children's Hospital of Fudan University. Interventions began at the study design stage, based on key scientific questions, clear design protocols, and statistical analysis methods based on the properties of the primary outcome indicators, whereby sample sizes were calculated based on expected effects. After study inclusion begins until the last patient data collection is completed, a detailed SAP is written and uploaded to the Clinical Trials Registry website. The following is an overview of the statistical analysis strategy and methods.

All analyses will be performed on an intention-to-treat (ITT) basis, except for sensitivity

analysis that will be performed according to per-protocol (PP) treatment.

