5.3.2 Analysis of primary outcome data

a) This study is non-inferiority trial design, and the primary outcome is the rate of OS at 5 years. The hypothesis is as follows:

Hypothesis: Let π_1 denote the rate of OS at 5 years in the open surgery group, and let π_2 denote the rate of OS at 5 years in the minimally invasive surgery group, the non-inferiority margin =8%. The null hypothesis is $H_0: \pi_1 - \pi_2 \geq$ versus the alternative hypothesis is $H_1: \pi_1 - \pi_2 <$.

b) The curves of OS at 5 years will be estimated using the Kaplan-Meier method. The logrank test will be used to test the above hypothesis, the 5-year OS rate difference and its 95% confidence interval (CI) for the comparison between the two groups will be estimated. The minimally invasive surgery will be considered non-inferior to the open surgery if the one-sided 95% upper limit is less than , where = 8%, the predetermined non-inferiority margin.

c) Covariate adjusted analysis:

An analysis of the primary outcome adjusting for the blood loss during operation, operative duration, and postoperative pain score will be performed using Cox proportional hazards regression model. The hazard ratio of 5-year OS and 95% CI will be estimated.

d) Subgroup analysis:

We will stratify by tumour staging, and perform Cox proportional hazards regression model to estimate the hazard ratio and 95% CI of the 5-year OS.

e) Sensitivity analysis:

A sensitivity analysis of the primary outcome will be performed using the PP strategy.

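### The only dated schedule gives patients 2 to 5 years of follow-up for a 5-year survival endpoint, and no trigger for the primary analysis is stated

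*Combined protocol and SAP*

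**What the plan says.** - Section 2.1 sets enrolment at three years, April 2021 to April 2024, and adds: "the patients will be followed-up for 5 years (April 2021 to April 2026".
- The timetable in section 3.10 has the same calendar. The row "Enrollment of study patients" is marked for months 0 to 36. Data analysis and "Summary and discussion" are marked only for months 36 to 60, and nothing runs past month 60.
- Section 3.12 states that "the primary outcome is the rate of OS at 5 years". Section 5.3.2 repeats this and decides non-inferiority on the upper confidence limit for the difference in five-year rates, while also saying "The logrank test will be used to test the above hypothesis".
- Section 3.7.3 leaves the end of visits undated: "After 2 years, the study will be reviewed every 6 months until the end of the trial".
- Section 7.3 schedules six-monthly visits up to the fifth year after surgery.
- Section 11.2 expects enrolment to need more than three years and follow-up to need at least five. It expects follow-up and analysis to continue for several years after the grant.
- Section 5.3.3 times only the interim analysis, at three years.
- Section 5.2.1 promises an SAP "uploaded to the clinical trial registry website before the last patient data collection is completed", and section 5.3.1 says much the same ("until the last patient data collection is completed, a detailed SAP is written and uploaded"). Neither gives a cut-off date, a minimum follow-up or a number of deaths for the primary analysis.

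**The concern.** The dated plan and the endpoint do not fit together. With enrolment open until April 2024 and follow-up closing in April 2026, most patients could not be observed to five years, so the primary endpoint would be unobserved for them. Other sections point to longer follow-up, but none gives a date.

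Two things are at stake. If the stated dates were applied, the five-year Kaplan-Meier difference would rest on a very thin tail and the power would be well below the planned 80%. And without a stated trigger, the data cut of a non-inferiority trial stays open to choice while results accumulate, so a reader cannot tell which power applies.

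**Working it through.** **1. The plan's own sample size.** Inputs from section 3.12: 72% in both arms, margin 0.08, one-sided 0.025, power 80%.

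n = (1.960 + 0.842)² × 2 × 0.72 × 0.28 / 0.08² = 494.5, so 495 per group. Check: SE = √(2 × 0.72 × 0.28 / 495) = 0.02854, and Φ(0.08/0.02854 − 1.96) = 0.800. For 10% drop-out, 495/0.9 = 550 per group, 1100 in total, rounded up to a multiple of 6 = 1104.

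The figure is correct. It is a binomial formula, so it takes five-year status as known for every evaluable patient and has no allowance for administrative censoring.

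**2. Follow-up implied by section 2.1.** First patient: April 2021 to April 2026, 5 years. Last patient: April 2024 to April 2026, 2 years. Under uniform accrual the mean is 3.5 years. The share with at least 4 years of potential follow-up is 1/3 (uniform), 1/9 = 11% (accrual rising linearly from zero) or 5/9 = 56% (falling linearly to zero).

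**3. Patients at risk in April 2026.** The assumed exponential hazard is −ln(0.72)/5 = 0.0657 per year. With uniform accrual and no loss:
- at 4 years, 1104 × 1/3 × exp(−0.0657 × 4) ≈ 283;
- at 4.9 years, 1104 × 1/30 × exp(−0.0657 × 4.9) ≈ 27;
- at 5 years, essentially none.

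**4. Power by cut-off.** Simulation of 552 per arm, 4,000 trials per scenario (Monte Carlo error about 0.8 points). Both arms have 72% at five years with exponential survival. Accrual over three years is uniform, rising or falling, and loss is 0 or 10% by five years. Follow-up is truncated at five years. The Kaplan-Meier test uses the Greenwood variance, with the last value carried forward in April 2026, and succeeds if difference + z × SE < 0.08. The hazard-ratio test uses a Cox model with margin ln(0.64)/ln(0.72) = 1.359, which assumes proportional hazards. The ranges below span accrual patterns and loss rates at one-sided 0.025.

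| Cut-off | Last patient followed | Kaplan-Meier difference | Hazard ratio |
|---|---|---|---|
| April 2026 | 2 years | 34–59% (uniform about 45%) | 56–69% (uniform 62–63%) |
| April 2027 | 3 years | 55–82% | 67–74% |
| April 2028 | 4 years | 77–84% | 71–75% |
| April 2029 | 5 years | 82–85% | 74–78% |

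Section 5.3.2 applies a one-sided 95% limit, which is looser than the 0.025 of section 3.12. On that limit, April 2026 gives 45–69% (uniform about 57%) for Kaplan-Meier and 68–80% (uniform 73–74%) for the hazard ratio. Weibull shapes of 0.8 to 1.2 widen the April 2026 Kaplan-Meier ranges to 30–63% at 0.025 and 41–73% at 0.05.

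**5. Check by expected deaths, no loss.** Power = Φ(√(deaths/4) × ln 1.359 − z). In April 2026, uniform accrual gives 225 deaths and power 63% (z = 1.960) or 74% (z = 1.645). Rising to falling accrual gives 197 to 254 deaths. With five years for all, 1104 × 0.28 = 309 deaths give 77% and 85%.

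**6. Reliability of the decision statistic in April 2026.** Under uniform accrual the median SE of the Kaplan-Meier difference is 0.042 to 0.043, against 0.027 to 0.028 in April 2029. Its mean is about 0.050, while the empirical SD of the difference is 0.057 or more, so the confidence limit would also tend to be too tight.

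**The case against.** The best defence is that this is an uncorrected date range. Section 2.1 says five years in words, section 7.3 schedules visits to year five, and section 11.2 plainly expects long follow-up. Section 5.2.1 puts data verification and database lock before analysis. Read with section 7.3, that suggests an analysis after the last patient's year-five visit. Nowhere is April 2026 declared to be the primary data cut-off, so the power loss is hypothetical and depends on accrual and survival patterns that the documents do not give. Kaplan-Meier estimation also handles censoring, and full five-year follow-up is not needed: a four-year minimum already gives about 80% on that scale.

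Much of this stands. The intent may well be longer follow-up, the power figures are conditional, and a trigger at five years for all is not the only one that power would allow. But the dates in section 2.1 are not an isolated slip, because the section 3.10 timetable repeats the same calendar and places analysis inside it. Together they are the only dated plan. The order of lock and analysis does not say when the lock happens, and the promised SAP is undated. An intention that must be inferred from several sections is not a pre-specified cut-off.

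**Conclusion.** The point holds. As written, section 2.1 and the section 3.10 timetable allow 2 to 5 years of follow-up per patient. This contradicts the five-year endpoint, the visits in section 7.3 and the expectations in section 11.2, and no section gives a trigger for the primary analysis. These findings come from the text and need no assumption.

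The size of the effect is conditional on an April 2026 cut-off. Kaplan-Meier power would then be roughly 45% instead of 80%, with a wide range by accrual and survival shape. On the hazard-ratio scale the fall is smaller, from about 77% to 63% without loss. The final alpha of 0.048 in section 5.3.3 is not used in these figures; moving from one-sided 0.025 to 0.024 lowers power by well under one point. Enrolment beyond April 2024, as section 11.2 expects, would lower power at April 2026 further. The sample size of 495 per group is not in error; the dates undermine the premise on which it rests. This should be corrected, not left to interpretation.

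**What to change.** Reconcile sections 2.1, 3.7.3, 3.10, 7.3 and 11.2, and state one pre-specified trigger in section 2.1, in the timetable and in the SAP. The trigger that best matches the rest of the plan is that the primary five-year survival analysis takes place when the last randomised patient has five years of follow-up. That means April 2029 if enrolment closes in April 2024, and later if enrolment overruns. Define the end of the trial in section 3.7.3 accordingly.

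If April 2026 has to stand, restate the power for that cut-off as a range with its assumptions, for the test actually used, and label that analysis preliminary. A four-year minimum (April 2028) is a middle course. It reports a year earlier with about 77% to 84% power on the Kaplan-Meier scale, but with incomplete five-year data.

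The textual change is a few dates and one sentence. The real cost is later reporting and up to three more years of follow-up for late enrollees, beyond the initial three years of funding. Section 7.3 already schedules those visits and section 11.2 already anticipates the longer work.

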2.2 Patient inclusion and exclusion criteria

Patient inclusion criteria:

- a) Clinical diagnosis of squamous carcinoma of the cervix, adenocarcinoma, squamous adenocarcinoma (stage IB3 and IIA2).
- b) Age ≥ 21 years and ≤ 70 years.
- c) Surgery type C (refer to Q-M surgical staging)

d) Normal range of liver and kidney function, and blood count:

Hemoglobin > 60g/L;

Platelets > 70*10⁹/L;

Leukocytes > 3*10⁹/L;

Creatinine < 50mg/dL;

Transaminase abnormal indicators ≤ 3;

Maximum value of transaminases not exceeding 3 times the corresponding normal value.

e) No history of other malignancies.

f) Non-pregnancy.

g) Physical strength classification: Karnofsky score ≥ 60.

h) Voluntarily join the study, sign the informed consent form, are compliant and cooperative with the follow-up.

i) No psychiatric disorders and other serious immune system disorders (e.g. lupus erythematosus, myasthenia gravis, HIV infection, etc.)

(Note: Maximum diameter measurement of cervical lesion is based on PET-CT, CT, or MRI)

Patient exclusion criteria:

a) Contraindicated for various surgeries and cannot undergo surgery.

b) Have received pelvic/abdominal radiotherapy irradiation or neoadjuvant chemotherapy for cervical cancer.

c) With recurrent cervical cancer

d) With CT, MRI or PET-CT suggesting suspicious metastasis of pelvic lymph nodes with maximum diameter >2cm after further improvement of preoperative examination.

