3.6 Post-operative adjuvant radiotherapy or radiochemotherapy

If the postoperative pathology report suggests the presence of risk factors associated with recurrence (high-risk factors or intermediate risk factors), postoperative adjuvant therapy is required if necessary.

(1) High-risk factors: positive parametrium, positive incisional margins, and positive pelvic lymph nodes.

Positive parametrium: external pelvic beam radiation therapy (EBRT) + cisplatin concurrent chemotherapy. Cisplatin (DDP) 40 mg/m²/w (week, w), or carboplatin if cisplatin is not tolerated (AUC=2). (If positive for parametrial tissue, local push of 5-10 Gy may be appropriate).

Positive vaginal incisional margins: external pelvic radiation therapy (EBRT) + cisplatin concurrent chemotherapy + vaginal backloading radiotherapy, with cisplatin (DDP) 40 mg/m²/w, or carboplatin (AUC=2) if cisplatin is intolerant.

Positive pelvic lymph nodes: one course of systemic chemotherapy + external pelvic radiation radiotherapy (EBRT) \pm extended field radiotherapy to the abdominal aorta + concurrent chemotherapy with cisplatin (40 mg/m²/w) + 3-6 courses of adjuvant systemic chemotherapy after radiotherapy (paclitaxel + cisplatin or carboplatin preferred

for large intravenous chemotherapy regimens, can use both domestic or imported). If the pathology confirms positive abdominal aorta or positive common iliac lymph nodes, irradiation of para-aortic extended field will be performed; when the pelvic lymph nodes are positive and the pathology result of abdominal aortalymph nodes clearance is negative (if only abdominal main biopsy without clearance, positive irradiation will be performed, negative is equivalent to no clearance), no extended field irradiation will be performed; if the lymph nodes in the pelvic lymph nodes are positive and the lymph nodes in the para-aortic lymph nodes are not cleared, but the image is suspected of metastasis in the para-aortic lymph nodes (full lymph nodes, length to diameter ratio close to 1), it is recommended to extend field irradiation.

(2) Intermediate risk factors (tumor size, interstitial infiltration, positive lymphovascular space), squamous carcinoma according to "Sedlis criteria": external pelvic radiation therapy (EBRT) + cisplatin concurrent chemotherapy, cisplatin (DDP) 40mg/m²/w.

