(4) More than 90% of the volume of HR-CTV per session is included in the prescribed dose range (6 Gy \times 3 sessions); for two-dimensional rear-loading radiotherapy plans, the prescribed dose point is 5 millimeters below the vaginal mucosa.

(5) The sum of external rectal irradiation and 2 Gy equivalent total dose (EQD2) of postoperative radiotherapy (2cc) is less than 65~75 Gy; sigmoid colon is less than 70-75 Gy, and bladder 2cc is less than 80~90 Gy.

The implementation of CCRT.

CCRT is given weekly cisplatin (DDP) intravenous chemotherapyduring EBRT. Cisplatin (DDP) 40 mg/m²/w is recommended for the first 3 days of the first week of radiotherapy initiation, with an expected 5 cycles.

Note: SEDLIS criteria

LVSI	Depth of interstitial invasion	Tumor size(cm) (determined by clinical gynecological examination)
+	Deep 1/3	Arbitrary
+	Medium 1/3	$\geq 2\text{cm}$
+	Shallow 1/3	$\geq 5\text{cm}$
-	Medium or deep 1/3	$\geq 4\text{cm}$

LVSI: Lymphovascular space invasion

3.7 Recording of follow-up data:

3.7.1 Preoperative assessment:

a) Standard preoperative laboratory tests determined by each center: (e.g., routine blood and urine test, coagulation function, blood liver, kidney function, electrolytes, HIV, RPR,

hepatitis markers)

- b) 12-lead ECG
- c) Tumor indicators: SCC antigen test (SCCA) and CA-125
- d) HPV typing test and TCT test in the last 3 months (only one preoperative test is required)
- e) Pathology or pathology consultation at each center (LEEP or conization is required for IA1 with LVSI and IA2).
- f) Imaging (CT scan of the chest, enhanced CT of the upper abdomen and pelvis, enhanced MRI to assess lesion size or PET-CT to assess retroperitoneal lymph node metastases)
- g) Collection of relevant medical history, height and weight, demographic data, and health insurance-related information of the patients
- h) Record all medications (including prescription drugs, over-the-counter drugs, vaccination, antibiotics, herbal medicine) used by the patient in the past 3 months
- i) Sign the informed consent form
- j) Record an inclusion criteria screening form
- k) Complete the randomization procedure, entering randomization codes for patients and recording the results
- l) Sign the informed consent form for the relevant surgery
- m) Patients may scan the QR code to register for the web-based follow-up platform

[Note]:

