3.8 Criteria for Patient Withdrawal

Patients have the right to withdraw from the trial treatment or study at any time without any reason. The investigator also has the right to withdraw a patient from the trial treatment or study in the event of secondary disease, adverse events, protocol violations, administrative reasons, or other reasons. Participation in the study, whether or not the affected patient participates, will not affect the relationship between the patient and the physician and will not result in a loss of medical or other benefits to the patient. However, in such cases, the investigator will make appropriate efforts to determine and document the reasons for the patient's voluntary withdrawal from the study. If a patient withdraws from the study, a complete final evaluation should be conducted at the time of patient withdrawal. This will be reported along with the study results and all attempts to locate patients lost to follow-up will also be documented.

Patients will be seen by their physician if they withdraw from the study. According to routine gynecologic oncology protocols, they should continue to receive care and treatment from an experienced physician until further follow-up is deemed unnecessary

by the treating physician.

Patients will be withdrawn from the study under the following circumstances:

- 1) Study completion/termination, or death
- 2) Patient demands withdrawal
- 3) Patient is unable or unwilling to cooperate with follow-up
- 4) Patient has other serious, non-surgical complications
- 5) Patient's follow-up information cannot be obtained
- 6) The study is terminated or cancelled at the request of the sponsor
- 7) Other relevant reasons

If a patient moves to another treatment center and requires changing of physician, the investigator will make a reasonable attempt to locate that center's physician and request cooperation in order to complete the follow-up.

In many cases, patient withdrawal from the study constitutes discontinuation of treatment and/or discontinuation of completion of related forms, such as quality of life. In these cases, the investigator should obtain the patient's permission to continue monitoring their disease status (relapse, survival, toxicity, etc.) through the patient's record.

Excessive exit rates can make a study uninterpretable, and therefore, unnecessary subject dropouts should be avoided.

3.9 Combination and simultaneous treatment:

[figure not shown]

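### The only numeric renal entry limit, a creatinine ceiling of 50 mg/dL, is about 33 to 63 times an assumed upper limit of normal and screens out practically nobody

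*Combined protocol and SAP*

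**What the plan says.** Section 2.2 of the combined protocol and SAP lists laboratory requirements under inclusion criterion d). The criterion opens with "Normal range of liver and kidney function, and blood count" and then gives individual limits. The renal one is "Creatinine < 50mg/dL". Neighbouring lines include "Hemoglobin > 60g/L" and "Maximum value of transaminases not exceeding 3 times the corresponding normal value".

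No other numeric renal threshold (clearance, eGFR or urea) appears anywhere in the documents. The remaining text that bears on renal fitness carries no number:

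- Section 2.2, exclusion a): "Contraindicated for various surgeries and cannot undergo surgery".
- Section 3.7.1, item a), which names kidney function among the "Standard preoperative laboratory tests determined by each center".
- Section 3.8: "The investigator also has the right to withdraw a patient from the trial treatment or study".
- Section 8.2, which provides for measures when adverse events occur and for a safety committee review twice a year.

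Section 3.6 plans cisplatin-based adjuvant treatment, in its words "If the postoperative pathology report suggests the presence of risk factors associated with recurrence".

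**The concern.** A serum creatinine ceiling of 50 mg/dL is far outside any range in which the test could separate fit from unfit patients. Taken literally, the line does no screening.

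The heading above it points the other way, because it asks for normal kidney function. The heading does not clearly settle the matter, since other lines in the same list accept values that are not normal: haemoglobin just above 60 g/L, and transaminases up to three times normal. In those cases the line, not the heading, is evidently the operative limit. A reader therefore cannot tell from the text which of the two governs creatinine.

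What is at stake is patient protection at entry to radical surgery, after which patients with pathological risk factors are planned to receive platinum. Six centres recruit (section 11.1), and a numeric criterion is there to give them one common threshold. As printed, this one does not. The point is limited to the printed value and unit. Renal fitness immediately before cisplatin, and the carboplatin alternatives, are separate matters.

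**Working it through.** The limit is a printed threshold, not a derived figure, so there is no calculation in the plan to reproduce. The check is whether the value can work as a serum creatinine limit.

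**Inputs**

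- Printed limit: 50 mg/dL (section 2.2, criterion d).
- Tolerance allowed for transaminases: 3 times normal (same criterion).
- Upper limit of normal (ULN) for serum creatinine: 0.8 to 1.5 mg/dL. This is an assumption; the documents give no value.
- Conversion: 1 mg/dL = 88.4 µmol/L. Also an assumption from outside the documents.

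**Step 1. Printed limit against the ULN (50 / ULN)**

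| Assumed ULN (mg/dL) | 50 / ULN |
|---|---|
| 0.8 | 62.5 |
| 1.0 | 50.0 |
| 1.2 | 41.7 |
| 1.5 | 33.3 |

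In SI units the limit is 50 × 88.4 = 4420 µmol/L, against an assumed ULN of 0.8 × 88.4 = 70.7 to 1.5 × 88.4 = 132.6 µmol/L.

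**Step 2. Printed limit against a looser yardstick**

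Suppose creatinine were allowed the same multiple as transaminases. The limit would be 3 × 0.8 = 2.4 to 3 × 1.5 = 4.5 mg/dL. The printed value is still 50/4.5 = 11.1 to 50/2.4 = 20.8 times that. The multiple is borrowed only for comparison; the plan does not apply it to creatinine.

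**Step 3. Can a reader recover the intended limit by changing the unit?**

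- If µmol/L was meant: 50/88.4 = 0.57 mg/dL, which is 0.57/1.5 = 0.38 to 0.57/0.8 = 0.71 of the ULN. This would turn away patients with normal values.
- If mg/L was meant: 5 mg/dL, which is 5/1.5 = 3.3 to 5/0.8 = 6.3 times the ULN, and 5/4.5 = 1.1 to 5/2.4 = 2.1 times the yardstick in step 2. This is still very loose.

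Neither obvious slip gives a workable limit, so centres cannot be expected to arrive at the same correction independently.

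**Step 4. Does another provision supply the missing limit?**

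| Provision | When it acts | Renal number? |
|---|---|---|
| Heading of criterion d), section 2.2 | Before entry | No; asks for normal function, but is overridden by other lines in the list |
| Exclusion a), section 2.2 | Before entry | No |
| Preoperative tests, section 3.7.1 | Before surgery | No; tests set locally |
| Investigator withdrawal, section 3.8 | After entry | No |
| Safety measures and review, section 8.2 | After entry | No |

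The first three are real screens but rest on local judgement. The last two come too late to act as entry criteria.

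**The case against.** The strongest reply is that the criterion is more than its number. Its heading is itself an inclusion requirement and names the kidney, so a patient with clearly abnormal renal function fails it whatever the line says. Exclusion a) removes patients unfit for surgery, and kidney function is measured beforehand. The haemoglobin and transaminase limits are loose but meaningful relaxations of the heading. A creatinine of 50 mg/dL is not, so an experienced surgeon would see a misprint and fall back on the heading. On this view the line is a drafting slip with no effect on either arm's results, and the heading already gives each centre a usable rule through its own laboratory range.

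Much of this stands. The documents do not show that any centre applied the figure literally or enrolled a patient in renal failure. Screening out practically nobody is a statement about the number, not about the whole criterion. Departure from the heading is not peculiar to creatinine; what is peculiar is the implausible value. An error of value or unit is far more likely than a deliberate choice. The criterion also applies before randomisation and equally to both arms.

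The reply does not rescue the line. Nothing elsewhere in the documents corrects it. If investigators ignore the number, the trial has no common numeric renal limit. If they defer to the heading, they must do so for creatinine while following the lines for haemoglobin and transaminases, and the text gives no instruction to that effect.

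**Conclusion.** The concern holds. The creatinine line is wrong as printed. On an assumed ULN of 0.8 to 1.5 mg/dL the ceiling is about 33 to 63 times normal, and the conclusion is the same anywhere in that range. The practical result is an ambiguous renal criterion with no usable common number, softened by the heading, exclusion a) and local testing.

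The number of patients affected cannot be derived from the documents. Nothing here bears on the sample size, the type I error or the primary comparison, and no actual harm is asserted. It is an eligibility error that should be corrected because the line is meant to protect patients.

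**What to change.** The sponsor should check the intended value and unit against its source and replace this one line. If the source cannot settle it, the limit should be written as a multiple of each centre's upper limit of normal, in the style of the transaminase line, with the multiple chosen by the sponsor's clinicians.

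The sponsor should also ask the six centres whether the printed limit was applied. Only if one says yes is it necessary to look at baseline creatinine already on file. This remains worthwhile if enrolment has closed, because it settles who was eligible.

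The cost is a one-line eligibility correction and one query to the centres, with a check of existing records only if needed. No new tests or visits are required.
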